11.0 Potential Benefits to Subjects and Others

11.1 Potential Benefits to Subjects

It is unclear whether liraglutide treatment will lead to any benefits in study subjects as no data are currently available. However, possible benefits the subject may experience from this research study include the possible reduction of opioid craving, which might improve their day-to-day function, and/or reduce near-term relapse to opioid abuse.

11.2 Potential Benefits to Others

The potential benefit to society and others includes increasing knowledge regarding the effects of liraglutide on clinical outcomes and its effect on the stress-immune response in acute hyperglycemic patients. New knowledge gained from this study could give way to novel treatments to help OUD recovery for a high-risk population.

12.0 Sharing Results with Subjects

Any clinically relevant study results (including, but not limited to, EKG and blood tests) will be shared with subjects and their treating physicians. No other study results of an individual subject's result will be shared with subjects or any treating physician.

13.0 Subject Payment and/or Travel Reimbursements

Participants will be reimbursement for their time in the amount of \$25 for the initial evaluation, \$50 for the first test day (Day 1, when fNIRs tasks and Cued response assessments are performed), \$50 for the 3-5 weeks (approximately 21-33 days) of EMA and physiological measures, \$75 for the second test day (Day 19) and \$50 for the third test day (Day 31) [5-dose intervention only]; when fNIRs tasks and Cued response assessments are performed), \$20 for the rebound follow-up, and \$30 for the follow-up phone call, for a total of \$250 (\$300 for 5-dose intervention). Payments will be titrated relative to the tasks accomplished. Reimbursements will be paid using Target gift cards because neither alcohol nor tobacco products can be purchased at Target.

14.0 Economic Burden to Subjects

14.1 Costs

There will be no added costs to the participants enrolled in this study. Any research-only laboratory tests and data collection procedures completed will be paid for by the research study.

14.2 Compensation for research-related injury

It is the policy of the institution to provide neither financial compensation nor free medical treatment for research-related injury. In the event of injury resulting from this research, medical treatment is available but will be provided at the usual charge. Costs for the treatment of research-related injuries will be charged to subjects or their insurance carriers.

15.0 Resources Available

15.1 Facilities and locations

All recruitment and study procedures will be performed at the CaronTC, a treatment facility in Wernersville, PA.

15.2 Feasibility of recruiting the required number of subjects

We have previously conducted three successful studies (two involving prescription opioids) at the CaronTC [50-55]. The professionals unit has 12 beds, and has typically had 30%-40% of those beds filled with patients with OUD. In addition, a recent census at CaronTC indicates a total of about 30 patients with OUD per month could be available for recruitment into the study from other units, which should be more than adequate to recruit the required sample size.

15.3 PI Time devoted to conducting the research

The PI has allocated sufficient time to work closely with the study team members. There will be regular meetings with study co-investigators to allow ongoing discussions, interim analyses and to address any operational issues.

15.4 Availability of medical or psychological resources

The CaronTC's Medical staff is available on a 24/7 basis.

15.5 Process for informing Study Team

The research team will be given specific duties to conduct the research study. The study coordinators will be provided with training to conduct the screening process, and instruct participants on how to use the equipment required for the study (actigraphs, smartphones). Staff members and nurses at Caron will be instructed on medication distribution and administration procedures. The PI and/or study coordinator will communicate updates to all team members as they become aware of any changes or updates.

16.0 Other Approvals

16.1 Other Approvals from External Entities

National Institute of Health (completed and approved)

16.2 Internal PSU Committee Approvals

Che	eck all that apply:
	Anatomic Pathology – Penn State Health only – Research involves the collection of tissues or use of pathologic specimens. Upload a copy of "HRP-902 – Human Tissue For Research Form" in CATS IRB.
	Animal Care and Use – All campuses – Human research involves animals and humans or the use of human tissues in animals
	Biosafety – All campuses – Research involves biohazardous materials (human biological specimens in a PSU research lab, biological toxins, carcinogens, infectious agents, recombinant viruses or DNA or gene therapy).
	Clinical Laboratories – Penn State Health only – Collection, processing and/or storage of extra tubes of body fluid specimens for research purposes by the Clinical Laboratories; and/or use of body fluids that had been collected for clinical purposes but are no longer needed for clinical use. Upload a copy of "HRP-901 – Human Body Fluids for Research Form" in CATS IRB.
	Clinical Research Center (CRC) Advisory Committee – All campuses – Research involves the use of CRC services in any way.
	Conflict of Interest Review – All campuses – Research has one or more of study team members indicated as having a financial interest.
	Radiation Safety – Penn State Health only – Research involves research-related radiation procedures. All research involving radiation procedures (standard of care and/or research-related) must upload a copy of "HRP-903 – Radiation Review Form" in CATS IRB.
	IND/IDE Audit – All campuses – Research in which the PSU researcher holds the IND or IDE or intends to hold the IND or IDE.
	Scientific Review – Penn State Health only – All investigator-written research studies requiring review by the convened IRB must provide documentation of scientific review with the IRB submission. The scientific review requirement may be fulfilled by one of the following: (1) external peer-review process; (2) department/institute scientific review committee; or (3) scientific review by

the Clinical Research Center Advisory committee. NOTE: Review by the Penn State Health Cancer Institute (PSCI) Protocol Review Committee or the PSCI Disease Team is required if the study involves cancer prevention studies or cancer patients, records and/or tissues. For more information about this requirement see the IRB website.

17.0 Multi-Site Study

- **17.1** Other sites

 Not applicable
- 17.2 Communication Plans
- 17.3 Data Submission and Security Plan
- 17.4 Subject Enrollment
- 17.5 Reporting of Adverse Events and New Information
- 17.6 Audit and Monitoring Plans

18.0 Adverse Event Reporting

18.1 Adverse Event Definitions

Adverse event	Any untoward medical occurrence associated with the use of the drug in
	humans, whether or not considered drug related
Adverse reaction	An Adverse Reaction is an adverse event for which the causal relationship
	between the drug and the adverse event is suspected.
Suspected adverse	Any adverse event for which there is a reasonable possibility that the drug
reaction	caused the adverse event. Suspected adverse reaction implies a lesser degree
	of certainty about causality than "adverse reaction".
	 Reasonable possibility. For the purpose of IND safety reporting,
	"reasonable possibility" means there is evidence to suggest a causal
	relationship between the drug and the adverse event.
Serious adverse	Serious adverse event or Serious suspected adverse reaction: An adverse event
event or Serious	or suspected adverse reaction that, in the view of either the investigator or
suspected adverse	sponsor, results in any of the following outcomes: Death, a life-threatening
reaction	adverse event, inpatient hospitalization or prolongation of existing
	hospitalization, a persistent or significant incapacity or substantial disruption
	of the ability to conduct normal life functions, or a congenital anomaly/birth
	defect. Important medical events that may not result in death, be life-
	threatening, or require hospitalization may be considered serious when, based
	upon appropriate medical judgment, they may jeopardize the patient or
	subject and may require medical or surgical intervention to prevent one of the
	outcomes listed in this definition. Suspicion of transmission of infectious
	agents must always be considered a serious adverse event.
Life-threatening	An adverse event or suspected adverse reaction is considered "life-
adverse event or	threatening" if, in the view of either the Investigator (i.e., the study site
life-threatening	principal investigator) or sponsor, its occurrence places the patient or research
suspected adverse	subject at immediate risk of death. It does not include an adverse event or
reaction	suspected adverse reaction that had it occurred in a more severe form, might
I I a a a a a a a a a a a a a a a a a a	have caused death.
Unexpected	An adverse event or suspected adverse reaction is considered "unexpected" if
adverse event or	it is not listed in the investigator brochure, not listed as per the reference
Unexpected	safety information (Prescribing information), or elsewhere in the current IND
	application; or is not listed at the specificity or severity that has been

suspected adverse	previously observed and/or specified. For the assessment of expectedness, a
reaction.	current version of the Prescribing information, or any updates thereof, would
	be used.

Unanticipated	Any serious adverse effect on health or safety or any life-threatening problem
adverse device	or death caused by, or associated with, a device, if that effect, problem, or
effect	death was not previously identified in nature, severity, or degree of incidence
	in the investigational plan or IDE application (including a supplementary plan
	or application), or any other unanticipated serious problem associated with a
	device that relates to the rights, safety, or welfare of subjects.

18.2 Recording of Adverse Events

All Aes (serious or non-serious) and abnormal test findings observed or reported to study team which are believed to be associated with the study drug will be followed until the event (or its sequelae) or the abnormal test finding resolves or stabilizes at a level acceptable to the investigator.

Pregnancy: Pregnancy complications will be recorded as AE. Outcome of the pregnancy will be followed up. If the infant has a congenital anomaly/birth defect this must be reported and followed up as an SAE. Any pregnancy occurring during the trial period will be reported to the IRB, NIDA, and Novo Nordisk within the same timelines described for reporting of AE.

18.3 Causality and Severity Assessments

The investigator will promptly review documented adverse events and abnormal test findings to determine 1) if the abnormal test finding should be classified as an adverse event; 2) if there is a reasonable possibility that the adverse event was caused by the study drug(s) or device(s); and 3) if the adverse event meets the criteria for a serious adverse event.

If the investigator's final determination of causality is "unknown and of questionable relationship to the study drug(s) or device(s)", the adverse event will be classified as associated with the use of the study drug(s) or device(s) for reporting purposes. If the investigator's final determination of causality is "unknown but not related to the study drug(s) or device(s)", this determination and the rationale for the determination will be documented in the respective subject's case history.

18.4 Reporting of Adverse Reactions and Unanticipated Problems to the FDA

18.4.1 Written IND/IDE Safety Reports

Not applicable

18.4.2 Telephoned IND Safety Reports – Fatal or Life-threatening Suspected Adverse ReactionsNot applicable

18.5 Reporting Adverse Reactions and Unanticipated Problems to the Responsible IRB

In accordance with applicable policies of The Pennsylvania State University Institutional Review Board (IRB), the investigator will report, to the IRB, any observed or reported harm (adverse event) experienced by a subject or other individual, which in the opinion of the investigator is determined to be (1) unexpected; and (2) possibly or probably related to the research procedures. Harms (adverse events) will be submitted to the IRB in accordance with the IRB policies and procedures.

In the event of an SAE or life-threatening adverse reaction, Caron medical staff will be immediately informed and address the situation. [name] and the medical monitor will be contacted within 12

hours. SAEs will be reported to the DSMB within 24 hours, and to the IRB within 10 days, of the PI's notification of the event. The need to suspend or modify the study procedures will be assessed with the IRB and DSMB. All non-serious Aes will be summarized and included in regular reports to the IRB and DSMB.

Reporting Adverse Reactions and Unanticipated Problems to NIDA

SAEs will be systematically evaluated at each clinic visit. Any SAE, whether or not related to study medication, will be reported to NIDA. SAEs that are "unexpected" and "possibly or probably related" to the research procedures will be reported to the IRB. The clinical PI, [name], will report any SAEs to NIDA within 72 hours of first becoming aware of the event. The initial SAE report will be followed by submission of a completed SAE report to NIDA. All SAEs will be followed until satisfactory resolution or until the site investigator deems the event to be chronic or the participant is stable.

Reporting of IRB actions to NIDA

Any actions recommended by the IRB will be reported to NIDA within 5 calendar days of the PI's notification.

Report of Changes or Amendments to the Protocol

Planned changes to the study will be reported and must receive approval from the Penn State IRB and NIDA prior to implementing these changes, except where necessary to eliminate apparent immediate hazards to the participants. In the case of changes implemented to eliminate immediate hazards to the participants, the emergency protocol changes will be reported to the IRB using a Reportable New Information submission. Electronic copies of all documents submitted to the IRB and NIDA will be maintained in the records. All research will continue to be conducted without inclusion of the modification until IRB and NIDA approval have been received.

Novo Nordisk safety reporting

The safety reporting requirement from Novo Nordisk states that, at minimum, all serious adverse reactions (SARs) and pregnancies occurring during the use of a Novo Nordisk product must be reported to Novo Nordisk. In addition to SARs, any other events that have been submitted to the health authorities according to local regulatory requirement must also be reported to Novo Nordisk at the time of submission to health authorities at the latest.

18.6 Unblinding Procedures

In case of a medical emergency, when the knowledge of the subject's treatment assignment may influence the subject's clinical care, the treating physician may contact Synergy Pharmacy to access the subject's treatment assignment. The research team members will document the reasons for unblinding in the subject's source documentation. Study team members will not share the information with personnel involved with the analysis and conduct of the study.

18.7 Stopping Rules

Blood pressure, heart rate, and respiratory rate will be measured on Days 1, 2, 8, 14, 19, and 21. On each day, each measure will be recorded 3-4 times and then averaged. Participants will be withdrawn if they experience an average daily value for any measure on Day 1, 2, 8, 14, or 19:

- Systolic blood pressure (SBP) changes >40 mmHg, or <90 mmHg or >200 mmHg, or clinical symptoms of hypertension (e.g. headache, dizziness, blurred vision, nausea edema) or hypotension (e.g. dizziness, nausea, fainting) develop
- Heart rate reaches levels <40 beats/min or >120 beats/min
- Respiratory rate changes by >5 breaths/minute or reaches levels <10 breaths/minute or >24 breaths/minute

The medical monitor will be alerted and immediate medical assistance will be sought from the medical staff at Caron if participants experience any of these events, or more serious AEs. The investigators will also exercise discretion to end an individual's study participation if they should engage in behavior that could jeopardize their own health and well-being or that of others.

Participants who develop any new conditions described in the exclusion criteria during the treatment phase of clinical trial will be removed from the study.

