1.4 Exploratory Endpoints

- 1) **Prefrontal Cortical Response to Drug Cues.** Change in blood oxygenation level response to visual opioid drug cues in prefrontal cortex from baseline (Day 1) to end of the target drug dose (Day 19 [additionally Day 31 for 5-dose intervention]) using Functional Near Infrared Spectroscopy (fNIRs).
- 2) **Rebound Ambient Drug Craving.** Change in ambient drug craving as measured by 0-100 VAS delivered via smartphone using the EMA on test days and on the first two days and last 2 days of each treatment dose from end of rebound follow up (Day 21 [Day 33 for 5-dose intervention]) to baseline (Day 1) and to end of the target drug dose (Day 19 [Day 31 for 5-dose intervention]).
- 3) **Rebound Blood Pressure.** Change in blood pressure from end of the target drug dose (Day 19 [Day 31 for 5-dose intervention]) to rebound follow up (Day 21 [Day 33 for 5-dose intervention]).
- 4) **Rebound Heart Rate.** Change in heart rate from end of the target drug dose (Day 19 [Day 31 for 5-dose intervention]) to rebound follow up (Day 21 [Day 33 for 5-dose intervention]).
- 5) **Rebound Respiration.** Change in respiratory from end of the target drug dose (Day 19 [Day 31 for 5-dose intervention]) to rebound follow up (Day 21 [Day 33 for 5-dose intervention]).
- 6) **Long-term Glycemic Control.** Change in HbA1c and fructosamine levels from Day 2 to end of the target drug dose (Day 19 [Day 31 for 5-dose intervention]).

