3.3 Early Withdrawal of Subjects

3.3.1 Criteria for removal from study

Blood pressure, heart rate, and respiratory rate will be measured on Days 1, 2, 8, 14, 19, and 21. On each day, each measure will be recorded 3-4 times and then averaged. Participants will be withdrawn if they experience an average daily value for any measure on Day 1, 2, 8, 14, or 19:

- Systolic blood pressure (SBP) changes >40 mmHg, or SBP <90 mmHg or >200 mmHg, or clinical symptoms of hypertension (e.g. headache, dizziness, blurred vision, nausea edema) or hypotension (e.g. dizziness, nausea, fainting) develop
- Heart rate reaches levels <40 beats/min or >120 beats/min
- Respiratory rate changes by >5 breaths/minute or reaches levels <10 breaths/minute or >24 breaths/minute

The investigators will also exercise discretion to end an individual's study participation if they should engage in behavior that could jeopardize their own health and well-being or that of others

Participants who develop any new conditions described in the exclusion criteria during the treatment phase of clinical trial will be removed from the study

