3.3.2 Follow-up for withdrawn subjects

Subjects will be withdrawn from the study if the study participant withdraws consent for any reason. The primary reason for the subjects' withdrawal from the study will be recorded.

Subjects who withdraw from the study may be replaced.

Subjects withdrawn due to pregnancy, adverse events (AEs), a medical emergency, or unwillingness or inability to comply with the protocol, will undergo an End of Study telephone call (30 days after the end of study treatment) unless the withdrawal is due to death or the withdrawal of consent.

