fNIRs data files will be placed into the REDCap database, with access to these files provided to key investigators at Drexel University for signal processing and return for data analyses. These data will be de-identified and will consist only of the unique study id number, raw data, stimulus markers, and date/time stamps that have been modified so that they do not contain the actual visit date.

- **Study drug/placebo administration:** Participants will be taught self-administration by study/nursing staff.
 - All self-administrations will occur via blinded, multi-dose subcutaneous injection pens, and will be observed by nursing staff at CaronTC.
 - Participants will receive medications daily at a specified time (prior to breakfast) throughout the study, starting on Day 2.
 - Participants will be taught to inject the solutions subcutaneously in the abdomen, thigh, or upper arm, and will administer daily injections under the supervision of a study nurse or staff member.
 - Participants will be taught by study staff nurses to attach the needle, check the drug/vehicle flow, select the dose, inject the dose, remove the needle, and dispose of the needle.
 - o Participants will always use a new needle for each dose administration in the study.
- Adverse Events: Adverse events will be monitored continuously throughout the study (Days 1-21 [Days 1-33 for 5-dose intervention]), and at 30 days post-intervention (Day 49 [Day 61 for 5-dose intervention]).

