7.2.5 Study Test Day – (Day 19)

The following **research-only** measures, all completed on Day 1, will be repeated on Day 19, regardless of intervention length (i.e., 3-dose and 5-dose interventions). Day 19 will serve as the final dose (1.8 mg) day for participants in the 3-dose intervention. For participants in the 5-dose intervention, Day 19 will be the final day at the 1.8 mg dose before moving on to the 2.4 mg dose on Day 20.

- Cardiorespiratory function will be assessed via measurement of blood pressure, heart rate, and respiratory rate as described in Section 7.2.
- Blood samples will be collected for safety laboratory tests (CBC, CMP) and for monitoring of glycemic control. Approximately 4 teaspoons of blood will be collected.
- Body weight data will be collected.

- Cue-elicited drug craving will be evaluated using VAS.
- Neurophysiology measurements will be evaluated using fNIRS during: (1) Visual cue reactivity and (2) BART.
- Collection of ambient drug craving, mood, and sleep data by EMA.
- Stress response, sleep, and activity measurements will be collected via actigraphy wristband.
- C-SSRS
- Urine pregnancy test (if applicable)
- Aes and concomitant medications will be documented.

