7.2.6 Days 20-21

For 3-dose intervention participants: Rebound Evaluation Period

During this time the following **research-only** measures will occur:

- Collection of ambient drug craving, mood, and sleep data by EMA through Day 21, then discontinued.
- Stress response, sleep, and activity measurements will be collected via actigraphy wristband through Day 21, then discontinued.
- Aes and concomitant medications will be documented through Day 21.
- Body weight data will be collected through Day 21.
- On Day 21, cardiorespiratory function will be measured as described in Section 7.2.

The smartphone and actigraphy wristband will be collected by a study coordinator on Day 22.

For 5-dose intervention participants: Study Drug Treatment, Dose 4

During this time, the following research-only activities will occur:

- During Days 20-21, 2.4 mg of liraglutide/placebo control will be administered daily at a specified time (prior to breakfast).
- Aes and concomitant medications will be documented.
- Ambient drug craving, mood, and sleep data will be collected on Days 20-21 via EMA assessment.
- Stress response, sleep, and activity measurements will be collected daily via actigraphy wristband.
- Body weight data will be collected daily.

On Day 20, cardiorespiratory function will be measured as described in Section 7.2.

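### A Day 19 vital-sign or symptom trigger can stop at most one of 18 doses in 3-dose participants, yet appears to end the Day 20-21 off-drug assessments that the rebound endpoints need

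*Combined protocol and SAP*

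**What the plan says.** Sections 3.3.1 and 18.7 carry the same rule. Limits are set for systolic pressure, heart rate and respiratory rate, together with symptoms of hypertension or hypotension, and "Participants will be withdrawn if they experience an average daily value for any measure on Day 1, 2, 8, 14, or 19" that breaches them. The heading of 3.3.1 is "Criteria for removal from study", so the rule reaches beyond study drug.

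On dosing, Section 7.2 states: "Participants will receive medications daily at a specified time (prior to breakfast) throughout the study, starting on Day 2". Section 7.2.5 adds: "Day 19 will serve as the final dose (1.8 mg) day for participants in the 3-dose intervention". For those who extend, "Day 19 will be the final day at the 1.8 mg dose before moving on to the 2.4 mg dose on Day 20".

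Days 20-21 are off drug for 3-dose participants. EMA, wristband, weight and adverse-event data continue, and "On Day 21, cardiorespiratory function will be measured as described in Section 7.2" (Section 7.2.6). Day 21 supplies the third timepoint of the secondary blood pressure, heart rate and respiration endpoints (Section 1.3). It also supplies the exploratory rebound endpoints in Section 1.4, for example "Change in heart rate from end of the target drug dose (Day 19 [Day 31 for 5-dose intervention]) to rebound follow up"; blood pressure and respiration have the same form, and rebound craving uses Day 21 as well.

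For people withdrawn for adverse events and several other reasons, Section 3.3.2 says they "will undergo an End of Study telephone call (30 days after the end of study treatment"). It names no other visit. The schedule gives the call to everyone who has not withdrawn consent; it collects adverse events and self-reported weight.

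**The concern.** Stopping rules normally trade lost data for reduced exposure. On Day 19 a 3-dose participant has almost no exposure left to avoid, while the off-drug observation is still to come. Read literally, the rule removes the Day 21 value because the Day 19 value of the same variable was extreme, or because symptoms appeared.

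The rebound endpoints are changes from Day 19 to Day 21. If Day 21 is absent for the participants furthest from baseline on Day 19, a summary of completers describes a selected group, and the selection may differ by arm. Section 10 lists effects of acute withdrawal from liraglutide and points to the rebound period as covering elimination, so these measurements are the protocol's own check on what happens after stopping.

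**Working it through.** **No figure in the plan bears on this point.** The documents give no SD and no expected trigger rate for any vital sign. The check is therefore a dose count from the documents, followed by an illustration whose inputs are assumed.

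**1. Doses a trigger can still stop.** There is one dose a day from Day 2. The 3-dose schedule has 19 − 2 + 1 = 18 doses; the 5-dose schedule has 31 − 2 + 1 = 30. The documents do not fix whether the vital signs precede that morning's dose, so two counts are given (measured after / before it).

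| Trigger day | 3-dose, of 18 | 5-dose, of 30 |
|---|---|---|
| 2 | 17 / 18 | 29 / 30 |
| 8 | 11 / 12 | 23 / 24 |
| 14 | 5 / 6 | 17 / 18 |
| 19 | 0 / 1 | 12 / 13 |

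The point is confined to participants who do not extend. For those who do, Days 20, 26 and 31 are not trigger days at all, so the two schedules select differently for their rebound data.

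**2. Illustration for respiratory rate.** From the documents: the limit is a change of more than 5 breaths/min. Assumed: change is measured from Day 1 and is normal with mean μ and SD σ; μ = −2 on liraglutide and 0 on placebo; the effect is fully gone by Day 21; the Day 19 and Day 21 changes have equal SD and correlation ρ of 0.5 to 0.8; Day 19 is the only trigger; the absolute limits and symptoms are ignored.

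With a = (−5 − μ)/σ and b = (5 − μ)/σ:
- proportion lost = Φ(a) + 1 − Φ(b)
- displacement of the mean Day 19 change among those kept: δ = σ[φ(a) − φ(b)] / [Φ(b) − Φ(a)]
- completers' mean rebound = −μ − (1 − ρ)δ (true value −μ = 2.0)
- completers' mean Day 1-to-21 change = ρδ (true value 0)

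Worked for σ = 3: a = −1.00, b = 2.33; lost = 0.159 + 0.010 = 0.168; δ = 3 × (0.2420 − 0.0262)/0.8315 = 0.78. Rebound = 2 − 0.5 × 0.78 = 1.61 for ρ = 0.5, and 2 − 0.2 × 0.78 = 1.84 for ρ = 0.8. Day 1-to-21 change = 0.39 to 0.62.

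| σ | Lost, liraglutide | Lost, placebo | δ | Completers' rebound (true 2.0) | Completers' Day 1-to-21 change (true 0) |
|---|---|---|---|---|---|
| 2 | 6.7% | 1.2% | 0.28 | 1.86 to 1.95 | 0.14 to 0.22 |
| 3 | 16.8% | 9.6% | 0.78 | 1.61 to 1.84 | 0.39 to 0.62 |
| 3.5 | 21.8% | 15.3% | 1.00 | 1.50 to 1.80 | 0.50 to 0.80 |

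If all 20 evaluable participants per arm (Section 8.2) followed the 3-dose schedule, σ = 3 would mean about 20 × 0.168 = 3.4 against 20 × 0.096 = 1.9 people.

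**3. Illustration for systolic pressure.** The limit is a change of more than 40 mmHg; assumed shift −5 mmHg, same formulas.
- σ = 15: a = −2.33, b = 3.00; lost 1.1%.
- σ = 20: a = −1.75, b = 2.25; lost 5.2%.

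The completers' rebound is 4.4 to 4.9 against a true 5.0. The heart-rate limits are absolute levels and the documents give no distribution, so nothing is computed for it.

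**4. Does the analysis repair it?** In a simulation of the respiratory case (σ = 3, shift of 2), regressing Day 21 on Day 19 among those kept and averaging the prediction over everyone returned 2.00 against a true 2.0. That works because the numeric limits act on an observed value. Symptom triggers need not behave so. Section 8.3 plans longitudinal methods for safety and rebound outcomes, but makes its missing-at-random statement for craving and gives no rule for Day 21 values lost to a trigger.

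**The case against.** Four arguments against the point deserve weight.

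- **The loss is inferred.** The instruction to cease study tasks (Section 3.3.3) is written for participants who themselves choose to stop medication. For a vital-sign trigger, the end of Days 20-21 follows from removal from the study and the absence of any other visit. This stands, and is why the remedy is reconciliation.
- **Clinical follow-up continues.** A reader might infer that nobody would learn whether these participants recover. The documents do not support that: Section 18.2 follows events and abnormal findings thought to be drug-related until they settle, and Section 18.7 brings in the medical monitor and medical staff. What is lost is the standardised research measurement.
- **Size and direction.** A reader might take the mean Day 19 change among those kept (−1.22 against −2.0 at σ = 3, 39% smaller) as the bias. But Day 19 has already been recorded when the trigger fires, and nothing says it is discarded; the rebound itself is 8% to 20% smaller in that case (1.84 and 1.61 against 2.0). A reader might also infer that liraglutide would look safer. That is unsupported: a smaller return from an on-drug shift means less apparent recovery, and the Day 1-to-21 comparison gains a spurious difference where none exists.
- **The example is favourable to the point.** It uses the tightest limit and a respiratory effect that no section supports. Section 2.2 describes a slight rise in heart rate and a modest fall in blood pressure, and the systolic example loses few people. Triggers on earlier days would also remove some participants before Day 19.

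In addition, the rebound changes are exploratory and this is a 50-patient pilot. These arguments limit the size; they do not explain why observation should end on a day when almost no drug remains to be stopped.

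**Conclusion.** The point holds for participants on the 3-dose schedule and should be addressed. A Day 19 trigger can prevent 0 or 1 of 18 doses, and as written it appears to cancel the Day 20-21 assessments. The Day 21 values are then missing selectively, on an extreme Day 19 value or on symptoms. Nausea, dizziness and headache are among the trigger symptoms, and Section 10 lists all three as liraglutide side effects, so loss may differ by arm for reasons the measured vital signs do not capture.

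The number affected cannot be derived from the documents. Under the assumptions stated, the respiratory limit costs 7% to 22% of the liraglutide arm and 1% to 15% of placebo their Day 21 value. The completers' rebound is then about 1.5 to 1.95 against 2.0, with a spurious Day 1-to-21 shift of about 0.1 to 0.8/min; losses for systolic pressure are about 1% to 5%. A model that includes Day 19 largely removes the bias for the numeric limits, but the plan does not specify one for these outcomes. The loss of data follows from the rule as written; how much bias results depends on the analysis.

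**What to change.** Reconcile Sections 1.4, 3.3.1, 3.3.2, 7.2.6 and 18.7 so that they separate what a trigger does to study drug from what it does to observation. State that when the trigger falls on the last-dose day, the Day 20-21 assessments already in the schedule are kept, with the participant's consent and where medical staff allow.

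In Section 8.3, include these participants in the rebound endpoints, using a longitudinal model that contains the Day 19 value, and say how Day 21 values missing after a numeric or a symptom trigger are handled. Add a safety table by arm: number and proportion meeting any vital-sign or symptom criterion, with the day and the triggering value or symptom, so that removed participants still count.

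The clinical limits, dosing and medical response are untouched. The cost is a short amendment, a sentence in the analysis section and one table. The downside is up to two more days of data collection for a few participants who are under medical review. Day 21 measurements that are not taken cannot be recovered later.
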